17.5 Other Safety or Tolerability Evaluations

17.5.1 ECG

The incidence and percentage of subjects with potentially clinically significant abnormalities (PCSA) for 12-lead Electrocardiogram (ECG) parameters will be summarized during the on-treatment period. The PCSA criteria are provided in [Table 8](#) below.

Table 8 Potentially Clinically Significant Abnormalities criteria for ECG

| Test | Potentially Clinically Significant Abnormalities (PCSA) Criteria |
|------------------------------------|---|
| Heart Rate (HR) | ≤ 50 bpm and decrease from baseline ≥ 20 bpm ≥ 120 bpm and increase from baseline ≥ 20 bpm |
| PR Interval | ≥ 220 ms and increase from baseline ≥ 20 ms |
| QRS | ≥ 120 ms |
| QTcF and QTcB absolute | Interval > 450 msec Interval > 480 msec Interval > 500 msec |
| QTcF and QTcB change from baseline | Increase from baseline > 30 msec Increase from baseline > 60 msec |

QTc will be corrected based on Fridericia's formula for QTcF and Bazett's formula for QTcB ($QTcF = QT / \sqrt[3]{RR}$ and $QTcB = QT / \sqrt{RR}$) where $RR=60/HR$. Baseline QTcF and QTcB will be derived from the visit that other ECG parameters are flagged as baseline. If there are multiple assessments at the same visit and time point, the average will be calculated for each parameter and used for the analysis.

Quantitative data for HR, PR, QRS, QTcF and QTcB will also be examined for trends using descriptive statistics (n, missing, mean, SD, median, Q1, Q3, minimum, maximum, and confidence interval) of actual values with 95% CI, absolute changes from baseline to each visit with 90% CI based on visit windows specified in [Section 11](#).

Listings of 12-lead ECGs will be provided with all relevant information and derived variables.

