7.1.3 End of Treatment

Discontinuation visit

For Part A, a discontinuation visit for safety evaluation should take place as soon as possible after the last administration of avelumab (at least within 7 days) in case treatment was discontinued because of the occurrence of an AE. For Part B, all subjects will have a Discontinuation visit regardless of the reason for discontinuation. The discontinuation visit consists of:

- documentation of AEs and concomitant medication;
- physical examination, including vital signs, and body weight;
- the 12-lead ECGs;
- the laboratory hematology, hemostaseology, and full serum chemistry, and basic urinalysis;
- CCI [REDACTED] CCI [REDACTED];
- ECOG PS; and
- PK sampling (subjects in Part B only).

End-of-Treatment visit

The End-of-Treatment visit is scheduled either 28 days (Part A) or 30 Days (± 5 days, Part B) after the last administration of avelumab, but before any new therapy is started, if possible, whichever occurs earlier. The End-of-Treatment visit will comprise a full assessment for safety, immunogenicity, and tumor response as appropriate, and will include the following (refer to [Appendix I](#)):

- The EQ-5D and FACT-M questionnaires
- AEs, and concomitant medications, ECOG PS
- Physical examination including vital signs, body weight, and skin tumor extent
- The 12-lead ECGs
- The laboratory hematology, hemostaseology, full serum chemistry, and full urinalysis (dipstick plus microscopic evaluation)
- The urine β -HCG pregnancy test (in females of childbearing potential)
- The tumor evaluation per 6 or 12 weekly schedule (only to be performed if no disease progression was documented previously)
- ACTH, ANA, ANCA, RF, T4, and TSH levels
- ADA sampling
- PK sampling (Part B only)
- CCI [REDACTED]
- CCI [REDACTED]
- CCI [REDACTED]

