- b Subjects with an adverse drug reaction ongoing at the End-of-Treatment visit and for any SAE suspected to be related to trial treatment occurring up to 3 months after the last dose of avelumab and thereafter will continue to be followed. Subjects without progressive disease at End-of-Treatment visit will be followed up for disease progression until PD (CT / MRI scans every 6 weeks; for trial sites in Germany, only MRI is to be used). In addition, subjects will be followed quarterly for survival (including assessment of any further tumor therapy). The survival follow-up will continue for up to 5 years after the last subject receives the last dose of avelumab, or last subject dies, whichever occurs earlier (see Section 7.1.5 for details).
- c Tumor evaluation at the End-of-Treatment visit should only be performed if no disease progression has been documented previously.
- d If another antineoplastic therapy is administered before the end of this 28-day period, the End-of-Treatment visit should be conducted, if possible, prior to the start of this new therapy.
- e The EQ-5D and FACT-M questionnaires should be completed by subjects at Screening, and prior to any study related procedures at Week 7, then once every 6 weeks thereafter while on treatment and at the End-of Treatment visit.
- f Subject interviews (optional; box on the Informed Consent Form indicating consent for interviews must be checked) will be conducted at Screening, Week 13, and 6 months (for both subjects on treatment and off treatment; see Section 7.7.1 for details). For subjects consenting to the interviews, a Contact Order Form including subject contact details will be completed and sent to the independent unit in charge of managing the interviews).
- g If the Screening ECOG PS was performed within 3 days prior to Day 1, it does not have to be repeated at Visit 1.
- h Enrollment will be done after the confirmation of fulfilling all screening inclusion criteria (Section 5.3.1) without matching any exclusion criterion (Section 5.3.2).
- i 12-lead ECG should be assessed during screening, prior to infusion and 2 hours \pm 20 minutes after the end of infusion at each visit on Days 1, 15, 29, 43, 57, 71, and 85 and every 6 weeks thereafter (until 18 months, after which on-treatment ECGs will not be required), at the Discontinuation / End-of-Treatment visit and Safety-Follow-up visit.

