- f Subject interviews (optional; box on the Informed Consent Form indicating consent for interviews must be checked) will be conducted at Screening, Week 13, and 6 months (for both subjects on treatment and off treatment; see Section 7.7.1 for details). For subjects consenting to the interviews, a Contact Order Form including subject contact details will be completed and sent to the independent unit in charge of managing the interviews).

- g A full physical examination should be performed at Screening and the Discontinuation visit (as required). Physical examinations at all other visits should be directed to signs and symptoms. Only subjects with liver metastases at Baseline are required to have a physical examination at Weeks 4 and 6.
- h If the Screening ECOG PS was performed within 3 days prior to Day 1, it does not have to be repeated at Visit 1.
- i Enrollment will be done after the confirmation of fulfilling all screening inclusion criteria (Section 5.3.1) without matching any exclusion criterion (Section 5.3.2).
- j 12-lead ECG should be assessed during screening and at the Discontinuation and End-of-Treatment visits.
- k Core serum chemistry is detailed in Table 7.
- l Full chemistry panel (including core chemistry) and other laboratory studies are detailed in Table 7. Follicle-stimulating hormone at Screening, if applicable (Section 7.1.1).
- m Full urinalysis (dipstick plus microscopic evaluation) at the Screening and End-of-Treatment visits and a basic urinalysis (dipstick only) at Day 1 visit prior to administration of study drug and at the Discontinuation and Safety Follow-up visits. If the basic urinalysis is abnormal, then a full urinalysis should be performed. Urinalysis after Day 1 should be performed as clinically indicated.
- n β -HCG should be determined from serum at Screening and from urine sample thereafter. Results of the most recent pregnancy test should be available prior to next dosing of study drug.

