Data after the cut-off date may not undergo the cleaning process and will not be displayed in any listings or used for summary statistics, statistical analyses or imputations.

Pooling of centers:

In order to provide overall estimates of treatment effects, data will be pooled across centers. The “center” factor will not be considered in statistical models or for subgroup analyses due to the high number of participating centers in contrast to the anticipated small number of subjects treated at each center.

Presentation of continuous and qualitative variables:

Continuous variables will be summarized using descriptive statistics i.e., number of non-missing values and number of missing values, [i.e., n (missing)], mean, median, standard deviation (SD), minimum, maximum and first and third quartile (Q1 and Q3).

Qualitative variables will be summarized by frequency counts and percentages. Unless otherwise stated the calculation of proportions will include the missing category. Therefore counts of missing observations will be included in the denominator and presented as a separate category.

In case the analysis refers only to certain visits, percentages will be based on the number of subjects still present in the study at that visit, unless otherwise specified.

Definition of baseline:

The last available assessment prior to the start of study treatment is defined as baseline measurement for both safety and efficacy analyses. If an assessment is planned to be performed prior to the first dose of study treatment in the protocol and the assessment is performed on the same day as the first dose of study treatment, it will be assumed that it was performed prior to study treatment administration, if assessment time point is not collected or is missing. If

assessment time points are collected, the observed time point will be used to determine pre-dose on study day 1 for baseline calculation. Unscheduled assessments will be used in the determination of baseline. However, if time is missing, an unscheduled assessment on study day 1 will be considered to have been obtained after study treatment administration.

Subjects who start treatment and discontinue from the study on the same day may have two different sets of data collected on study day 1 (one during study and one in the End of Treatment (EOT) visit). Data reported at the EOT visit are not eligible for baseline selection.

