Data collected at unscheduled visits will be included and analyzed for both safety and efficacy analyses in the same fashion as the data collected at scheduled visits except where otherwise noted in the sections that follow. Descriptive statistics (mean, SD, median, minimum, maximum and quartiles) by nominal visit or time point for safety endpoints such as laboratory measurements, ECGs and vital signs will include only data from scheduled visits.

Summary statistics over time:

For descriptive statistics over time by nominal visit or time point for QoL, laboratory assessment, and vital sign data, only those planned visits/time points that have at least 5 subjects will be included in the summary tables and figures. The exception is the Discontinuation and End-of-Treatment visits, which will be included in the summary statistics regardless of the number of subjects who completed the visit.

Data collected after re-initiated treatment:

Data collected after re-initiation of treatment will only be included in the data listing. It will not be included for safety and efficacy summary analyses except for overall survival and disposition.

Visit window:

The assignment of visit window is described in [Table 2](#) for the purpose of by-visit analyses of laboratory assessment and vital sign data:

- Baseline will be derived as described above.
- Both scheduled and unscheduled assessments are included for visit windowing.
- No visit windowing will be performed at Discontinuation, End-of-Treatment, or Safety Follow-up visits for laboratory and vital sign data. Instead, the earliest non-missing observation among the unscheduled or scheduled assessments for each visit (Discontinuation, End-of-Treatment, and Safety Follow-up) will be used for the analysis.
- If there are multiple assessments for any specified visit and some of them are from scheduled visits with non-missing assessment results, the assessment from scheduled visit that is closest to the planned study day will be used for analysis.
- If there are multiple assessments for any specified visit and none of them are from scheduled visits, the assessment with non-missing results and closest to the planned study day will be used for analysis.

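### Part B schedules no ECG during dosing, yet the SAP's on-treatment ECG abnormality percentages, read with its default rule, keep subjects with no post-baseline ECG in the denominator

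*SAP*

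**What the plan says.** **Schedule.** Protocol Appendix I, Part B, footnote j: "12-lead ECG should be assessed during screening and at the Discontinuation and End-of-Treatment visits". The Part B table and Protocol 7.1.4 add the 90-day Safety Follow-up visit, which the footnote omits. The table marks no ECG from Week 1 to Week 13 or in the until-progression column, and the treatment-period list in 7.1.2.2 contains none. Part A differs: its footnote i starts "12-lead ECG should be assessed during screening, prior to infusion and 2 hours" and runs through every treatment visit to Week 13, then six-weekly to 18 months.

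**Analysis.** Part B SAP 17.5.1 states that the "incidence and percentage of subjects with potentially clinically significant abnormalities (PCSA) for 12-lead Electrocardiogram (ECG) parameters will be summarized during the on-treatment period". It also gives "absolute changes from baseline to each visit with 90% CI based on visit windows specified in" Section 11. Section 11 sets those windows up "for the purpose of by-visit analyses of laboratory assessment and vital sign data", and its Table 2 has no ECG row. The modification history for version 3.0 records that ECG was taken out of visit windowing.

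**Denominator.** Section 17 uses the Safety analysis set, which Section 10 defines as everyone given at least one dose. Unless a section says otherwise, Section 11 applies: "counts of missing observations will be included in the denominator and presented as a separate category". Section 17.5.1 says nothing different. Section 17.3.1 does: it excludes subjects without post-baseline laboratory samples.

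**On-treatment period.** Section 11 ends it 30 days after the last dose, or the day before a new anticancer drug begins if that is sooner.

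**The concern.** In Part B a post-baseline ECG is triggered by stopping treatment. A subject who continues on avelumab has none scheduled, however long the exposure. If such subjects stay in the denominator of a PCSA percentage, they count in effect as subjects without an abnormality, although nobody has looked.

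The direction is known: every PCSA percentage is pulled down. ECG parameters are listed among the safety endpoints in Protocol 8.3.3, and Protocol 5.1 describes Part B as the confirmatory study for some approvals, so the table is likely to be read as evidence on cardiac safety. The reference to windows that do not exist for ECG is a separate, smaller defect: a programmer following 17.5.1 would find no rule to apply.

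**Working it through.** The documents state no ECG rate and no ECG denominator, so there is no figure of the plan's own to reproduce. The check has three steps.

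**1. Can subjects be on treatment at the cut-off with no scheduled post-baseline ECG?** Yes.
- The Discontinuation visit happens only on stopping: "For Part B, all subjects will have a Discontinuation visit regardless of the reason for discontinuation" (Protocol 7.1.3).
- SAP 12.1 has a disposition line for subjects still on treatment.
- The primary cut-off is 15 months after the last subject's first dose (SAP 8): 15 × 30.4375 = 456.6, about Day 457.
- SAP Section 6 foresees at least 12 months of treatment after a confirmed complete response. For the last subject enrolled, a response confirmed at Week 19 (Day 127) runs to 127 + 365.25, about Day 492, past the cut-off.
- Two-weekly dosing over 15 months gives 33 infusion visits (456.6/14 = 32.6, so 32 complete intervals plus the first dose). None carries a scheduled ECG.

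**2. Size of the effect.** Let N be the Safety set, k the subjects without a post-baseline ECG, and p the PCSA rate among the N − k subjects with one. Then

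reported percentage = p × (N − k)/N.

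N = 112 is the planned size. The share still on treatment and the values of p are assumptions, and no unscheduled ECG is assumed for these k subjects. The last column is the exact two-sided 95% upper limit for zero events, 1 − 0.025^(1/n), with n = N − k.

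| Share without ECG | k | N − k | p = 10% reported as | p = 20% reported as | Upper limit, zero events |
|---|---|---|---|---|---|
| 0% | 0 | 112 | 10.0% | 20.0% | 3.2% |
| 10% | 11 | 101 | 9.0% | 18.0% | 3.6% |
| 20% | 22 | 90 | 8.0% | 16.1% | 4.0% |
| 30% | 34 | 78 | 7.0% | 13.9% | 4.6% |
| 40% | 45 | 67 | 6.0% | 12.0% | 5.4% |

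For example, with k = 22: 10% × 90/112 = 8.0%. Dividing by N − k instead of N restores p in every row.

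**3. Which ECGs fall in the on-treatment period?** A Discontinuation ECG, taken within 7 days of the decision to stop, normally falls within 30 days of the last dose. The End-of-Treatment window is 30 ± 5 days, Days 25 to 35. Days 25 to 30 are inside and Days 31 to 35 are outside, that is 5 of 11 permitted days. The 90-day Safety Follow-up ECG is outside.

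**The case against.** The strongest reply is that the denominator is inferred. Section 17.5.1 names none, and Section 11 also has a rule that percentages tied to particular visits use the subjects still in the study at that visit. That rule is written for visit-specific tables, whereas the PCSA table covers a period, so the general default is the more natural reading. The point stands that the SAP leaves it to inference, which is itself a reason to state the denominator.

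Other parts of the reply hold and limit the point:

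- **Not hidden.** The default shows missing subjects as a separate category, and 17.5.1 lists the number missing for the quantitative data. A reader can recompute the rate.
- **Not every continuing subject.** Section 11 includes unscheduled data in safety analyses, so an ECG taken for clinical reasons during dosing can count toward PCSA.
- **By-visit statistics are already restricted.** The Section 11 rule on unscheduled visits names ECGs and confines by-visit descriptive statistics to scheduled visits. In Part B those are Discontinuation, End of Treatment and Safety Follow-up. What is wrong is the cross-reference, and also that the Section 11 rule for choosing the value at those three visits covers only laboratory and vital-sign data.
- **The vital-signs contrast is partial.** Section 17.4 limits its summaries to subjects with post-baseline values but also keeps a missing category. The laboratory contrast is clear.
- **Limited weight.** The analysis is descriptive, full ECG listings are planned, and the Part B secondary endpoints in Protocol 5.1.2.2 do not name ECG parameters, although the Part A list does.

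A reader might go further and infer that the on-treatment table would be empty, or would describe only ECGs taken off drug. The documents do not support this: Discontinuation ECGs and most permitted End-of-Treatment days lie within the SAP's on-treatment period. Nor do 5 excluded days of 11 mean that 5 in 11 subjects are lost. These are calendar days, and a subject seen on Days 31 to 35 should already have a Discontinuation ECG.

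**Conclusion.** The point holds in a limited form. Part B has no scheduled ECG between Screening and Discontinuation. Under the SAP's default rule, the on-treatment PCSA percentages are lowered by the factor (N − k)/N. With 10% to 40% of 112 subjects lacking a post-baseline ECG, the factor runs from 0.90 to 0.60. This range is an assumption: the documents give neither the share still on treatment nor a PCSA rate. The calculation also assumes that the Section 11 default governs 17.5.1 and that the k subjects have no unscheduled ECG. The factor may be lower at the interim three months after the 25th subject's accrual, when SAP 8.2 also runs the safety analyses. The stale window reference is certain and rests on no assumption.

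It would be tempting to relabel the whole table as post-treatment and pool every ECG up to Safety Follow-up. That does not follow. It would bring in recordings made after a new anticancer drug, which the on-treatment rule excludes, and would mislabel ECGs that the protocol (8.5.4) counts as on treatment.

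**What to change.** In Part B SAP 17.5.1:

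1. Keep the on-treatment period, but take as PCSA denominator the subjects with at least one post-baseline on-treatment ECG. For criteria based on change, also require a baseline ECG. Report the number of treated subjects with none.
2. Replace the reference to the Section 11 windows with change from baseline at the scheduled Discontinuation, End-of-Treatment and Safety Follow-up visits. Show the Safety Follow-up ECG, and any ECG later than 30 days after the last dose or after a new anticancer drug, apart from the on-treatment PCSA table.
3. Add a footnote to the table that Part B has no scheduled ECG during dosing.

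The Part B schedule table and footnote j should also be reconciled on the Safety Follow-up ECG. The cost is SAP wording and one denominator flag, and these SAP changes call for no additional ECG. The downside is a smaller n and slightly less favourable percentages.

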17.5.2 ECOG Performance Status

The ECOG shift from baseline to highest score during the on-treatment period will be summarized. ECOG performance status with shift from ECOG=0 or 1 to ECOG=2 or higher will also be presented in a data listing with subject identifier and other relevant information.

17.5.3 Immunogenicity

ADA was assessed before the trial treatment start, and on Days 15, 29, 43, and 85 prior to the start of infusion, then every 6 weeks until Week 25, and every 12 weeks thereafter. ADA was also assessed at the End-of-Treatment and Safety Follow-up visits. If the sample is positive for ADA, it will be re-analyzed to determine the titer and nAb. The ADA results will be derived based on the algorithm in Table 9. Subjects will be characterized into different ADA categories based on the criteria in

Table 10.

Table 9 Algorithm for the Derivation of ADA Results

| Sample Screen Result | Confirmatory | Titer | ADA Result |
|----------------------|--------------|--------|--------------|
| Negative | NA | NA | Negative |
| NR | NA | NA | NR |
| Positive | Negative | NA | Negative |
| Positive | NR | NA | NR |
| Positive | Positive | Number | Number |
| Positive | Positive | NR | Positive-TNR |

NR = no result, NA = not applicable, TNR = titer no result.

Negative, number, or positive-TNR are valid results, while number and positive-TNR are considered as positive.

Table 10 Subjects Characterized based on ADA Results

| Category | Definition | Subject at Risk (Denominator for Incidence) |
|--------------------|--|---|
| Never positive | No positive results at any time point | Number of subjects with at least one valid result at any time point |
| Ever positive | At least one positive result at any time point | Number of subjects with at least one valid result at any time point |
| Pre-existing | A positive ADA result prior to treatment with avelumab | Number of subjects with valid baseline result |
| Treatment boosted | A positive ADA result prior to treatment with avelumab and the titer $\geq 8 \times$ baseline titer while on avelumab treatment | Number of subjects with valid baseline and at least one valid post-baseline result |
| Treatment emergent | Not positive prior to treatment with avelumab and with at least one positive post-baseline result | Number of subjects with at least one valid post-baseline result and without positive baseline results (including missing, NR) |
| Transient positive | If treatment emergent subjects have (a single positive evaluation, or duration between first and last positive result <16 weeks) and last assessment not positive. | Number of subjects with at least one valid post-baseline result and without positive baseline results (including missing, NR) |

| Category | Definition | Subject at Risk (Denominator for Incidence) |
|---------------------|---|---|
| Persistent positive | If treatment emergent subjects have duration between first and last positive result ≥ 16 weeks or a positive evaluation at the last assessment | Number of subjects with at least one valid post-baseline result and without positive baseline results (including missing, NR) |

Samples with a reportable ADA titer will also be tested in the neutralizing antibody (nAb) assay. nAb results are positive or negative in a single assay and only derived when not performed because ADA was negative (see Table 11). Subjects will be characterized into different nAb categories based on the criteria in Table . For nAb, treatment-boostered is not applicable since no titer result is available.

Table 11 Algorithm for the Derivation of nAb Results

| ADA Confirmatory Result | nAb Result | Derived nAb Result |
|-------------------------|------------|--------------------|
| Negative | NA | Negative |
| NR | NA | NR |
| NA | NA | Negative |
| Positive | NR | NR |
| Positive | Positive | Positive |
| Positive | Negative | Negative |

ADA = antidrug antibody, NA = not applicable, nAb = neutralizing antibody, NR = no result.

Table 12 Subjects Characterized based on nAb Results

| Category | Definition | Subject at Risk (Denominator for Incidence) |
|---------------------|---|---|
| Never positive | No nAb positive results at any time point | Number of subjects with at least one valid ADA result at any time point |
| Ever positive | At least one nAb positive result at any time point | Number of subjects with at least one valid ADA result at any time point |
| Pre-existing | A positive nAb result prior to treatment with avelumab | Number of subjects with valid ADA baseline result |
| Treatment emergent | Not nAb positive prior to treatment with avelumab and with at least one nAb positive post-baseline result | Number of subjects with at least one ADA valid post-baseline result and without nAb positive baseline results (including missing, NR) |
| Transient positive | If treatment emergent subjects have (a single nAb positive evaluation, or duration between first and last nAb positive result < 16 weeks) and last ADA assessment not nAb positive. | Number of subjects with at least one ADA valid post-baseline result and without nAb positive baseline results (including missing, NR) |
| Persistent positive | If treatment emergent subjects have duration between first and last nAb positive result ≥ 16 weeks | Number of subjects with at least one ADA valid post-baseline result and without nAb |

| Category | Definition | Subject at Risk (Denominator for Incidence) |
|----------|---|---|
| | or a nAb positive evaluation at the last ADA assessment | positive baseline results (including missing, NR) |

ADA = antidrug antibody, nAb = neutralizing antibody, NR = no result.

The frequency and percentage of each ADA and nAb category will be presented in tables. Listings of ADA and nAb results from ADA ever positive subjects will be prepared.

For the ADA ever-positive subjects, a listing will be prepared with subject ID, start and stop of treatment, date of onset, time to onset (weeks since treatment start) and last date of ADA positive results, as well as date of onset, time to onset and last date of nAb positive results, BOR and BOR date, DOR, PFS time or censoring time and reason for censoring, and OS time or censoring time and reason for censoring.

For the ADA ever-positive subjects, the percent change from baseline in target lesions as well as the first occurrence of a new lesion and subject off treatment will be displayed against time point (weeks) in a line plot. Additional symbols will indicate the first and last ADA positive result and, if applicable, the first and last nAb positive result.

18 **References**

5. Beal S. L. Ways to fit a PK model with some data below the quantification limit. *J Pharmacokin Pharmacodyn.* 28: 481 – 504 (2001).

19 Appendices

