8.5.3.4 Serum Titers of Anti-Avelumab Antibodies (ADA)

Immunogenicity testing strategy will be implemented and conducted in line with:

- Immunogenicity Assessment of Biotechnology-Derived Therapeutic Proteins ([EMA/CHMP/BMWP/14327/2006](#))
- Immunogenicity assessment of monoclonal antibodies intended for in vivo clinical use ([EMA/CHMP/BMWP/86289/2010](#))
- FDA Guidance for Industry: Assay Development for Immunogenicity Testing of Therapeutic Proteins ([FDA; December 2009, draft](#))

A qualified method that uses an acid dissociation step to detect antidrug antibodies in the presence of excess drug in human serum will be applied. The ADA titers of positive samples will be determined. Positive samples will be analyzed for neutralizing capability.

CCI

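### Part B SAP 17.5.3: Tables 11 and 12 mishandle samples and subjects with no nAb result, so ever-positive nAb incidence can be understated

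*SAP*

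**What the plan says.** All references are to Part B SAP section 17.5.3 unless stated otherwise.

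- **ADA result (Table 9).** A sample passes through screen, confirmatory test and titer. A negative screen and a screen with no result (NR) both carry a confirmatory entry of NA. The first ends as ADA Negative, the second as ADA NR. A confirmed positive without a titer has its own row: "Positive | Positive | NR | Positive-TNR". The note to the table says "Negative, number, or positive-TNR are valid results, while number and positive-TNR are considered as positive".
- **Which samples are assayed for nAb.** The opening of the section says "If the sample is positive for ADA, it will be re-analyzed to determine the titer and nAb", and protocol 8.5.3.4 says "Positive samples will be analyzed for neutralizing capability". The text before Table 11 says "Samples with a reportable ADA titer will also be tested in the neutralizing antibody (nAb) assay".
- **Derived nAb result (Table 11).** The text says "nAb results are positive or negative in a single assay and only derived when not performed because ADA was negative". The table is keyed on the confirmatory result. It keeps confirmatory NR as NR, and confirmatory Positive with nAb NR as NR. It also contains the row "NA | NA | Negative".
- **Subject categories (Table 12).** Never positive means that no nAb-positive result was seen. The denominator for never and ever positive is "Number of subjects with at least one valid ADA result at any time point". Transient positive requires, among other things, that the last ADA assessment was not nAb-positive. The treatment-emergent risk set keeps subjects whose baseline result is missing or NR.

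**The concern.** An nAb-positive subject must be ADA-positive. If ADA-positive subjects without an nAb result are placed with the negatives, the group in which a positive could occur is diluted by missing data, and the table does not show it. Three rules need checking: the NA row of Table 11, the choice of samples to assay, and the categories of Table 12.

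Evaluating immunogenicity is a secondary objective of Part B, the nAb category frequencies are to be tabulated, and the protocol (5.1) calls Part B the confirmatory study for some approvals. A reader of the report would take the nAb incidence at face value.

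**Working it through.** The documents state no nAb incidence, ADA-positive rate or missing-result rate, so there is no planned figure to reproduce. The check passes every Table 9 path through Table 11 and then applies Table 12.

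**Step 1. Sample paths.**

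| Screen | Confirmatory | ADA result | nAb assay | Table 11 gives | Comment |
|---|---|---|---|---|---|
| Negative | NA | Negative | not done | Negative | correct |
| NR | NA | NR | not done | Negative | wrong: ADA status unknown |
| Positive | Negative | Negative | not done | Negative | correct |
| Positive | NR | NR | not done | NR | correct |
| Positive | Positive | titer | Positive | Positive | correct |
| Positive | Positive | titer | Negative | Negative | correct |
| Positive | Positive | titer | NR | NR | correct |
| Positive | Positive | Positive-TNR | not done | no row | undefined |

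One path is coded against the SAP's own text, and one has no rule.

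**Step 2. Effect of the screen-NR path.** The ever/never-positive denominator in Table 12 needs a valid ADA result, and NR is not valid. Recoding such a sample from Negative to NR leaves the never-positive, ever-positive, pre-existing and treatment-emergent counts unchanged. The sample record is wrong. If that sample counts as the last assessment, a subject whose last usable nAb result was positive, with first and last positives less than 16 weeks apart, moves from persistent to transient.

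**Step 3. Effect of a missing nAb result in an ADA-positive subject.** The subject has a valid ADA result and no nAb-positive result, so Table 12 counts never positive. The NR that Table 11 preserved is lost. With all 112 planned subjects in the denominator, each truly nAb-positive subject missed costs 1/112 = 0.9 percentage points.

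**Step 4. Size under assumptions.** Let a be the ADA ever-positive share, q the true nAb share among ADA-positive subjects, and f the share of ADA-positive subjects with no nAb result, independent of nAb status.

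- True incidence: a × q.
- Incidence as planned: a × q × (1 − f). The shortfall is a × q × f, so the relative understatement equals f.

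The ranges below are assumed: a = 5–20%, q = 25–50%, f = 0–30%.

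- f = 0: no shortfall.
- f = 10%: from 0.05 × 0.25 × 0.10 = 0.125 points to 0.20 × 0.50 × 0.10 = 1.0 points.
- f = 30%: from 0.05 × 0.25 × 0.30 = 0.375 points to 0.20 × 0.50 × 0.30 = 3.0 points.

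**Step 5. Would another denominator repair it?** Dropping unresolved subjects gives a × q × (1 − f)/(1 − a × f). At the extreme (a = 20%, q = 50%, f = 30%) this is 0.07/0.94 = 7.45%, against 7.00% as planned and 10.0% true. Most of the shortfall remains.

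Bounds are more informative. Take a hypothetical 112 ADA-valid subjects, 4 nAb-positive and 2 ADA-positive with no nAb result. The plan reports 4/112 = 3.6%, and the data support anything from 3.6% to 6/112 = 5.4%.

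**Step 6. Opposite direction.** A subject who is truly nAb-positive at baseline, has nAb NR then, and tests positive later meets the treatment-emergent definition. That category can therefore be overstated.

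**The case against.** Several parts of the opposing case stand.

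- The sentence on when nAb is derived is correct: without anti-drug antibody there can be no neutralizing anti-drug antibody. A reader might take that derivation as the source of bias, but it causes none. The fault lies in the tables.
- A reader might infer that coding screen-NR samples as Negative lowers the incidence. By Step 2 it does not. Even the persistence effect depends on reading the last assessment to include a sample with no result, which the SAP leaves open.
- The sentence on samples with a titer does not say that other samples are excluded. It conflicts with the section's opening and with protocol 8.5.3.4, but it does not prove that Positive-TNR samples go untested. If they are tested, or recorded as nAb NR, existing Table 11 rows apply. Only 'not done' lacks a row.
- Missing nAb results would be visible in the planned listings of ADA and nAb results for ADA ever-positive subjects.
- The secondary endpoint names anti-avelumab antibody titers, not nAb, and these tables are descriptive.

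None of this answers Step 3. Table 10 requires a valid result for the antibody it reports. Table 12 does not, and it has no place for a subject whose nAb status is unknown. A listing does not correct the frequency in the table.

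**Conclusion.** The point holds in a limited form. Followed as written, Table 11 miscodes screen-NR samples, the plan conflicts on which positives are assayed, and Table 12 reports ADA-positive subjects with no nAb result as never nAb-positive. Ever-positive nAb incidence can then be too low, by about 0.9 percentage points of 112 per truly nAb-positive subject missed. The shortfall is zero if every ADA-positive subject has nAb results on the positive samples. The larger figures in Step 4 rest on assumed rates.

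Three stronger readings are tempting, and the documents do not support them.

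- That the incidence is biased low. It can be; no count of missing nAb results is given.
- That the error always runs one way. Treatment-emergent nAb can be overstated (Step 6).
- That each missed subject costs 6 to 17 points. That figure is 1/17 to 1/6 of the ADA-positive subjects, under an assumed ADA rate of 5–15% of 112. Table 12 divides by ADA-valid subjects.

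The correction is worth making because a stated rule misclassifies subjects, but it touches only a descriptive immunogenicity table. The primary durable response analysis is unaffected.

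**What to change.** 1. Key Table 11 on the final ADA result of Table 9. ADA Negative gives nAb Negative. ADA NR gives nAb NR. ADA positive, including Positive-TNR, gives the assay result, or NR if the assay was not done.
2. Align the sentence on samples with a titer with the opening of 17.5.3 and with protocol 8.5.3.4, so that all ADA-positive samples go to the nAb assay.
3. In Table 12, show ADA-positive subjects with no nAb result on any positive sample as a separate 'nAb unknown' category. Give a lower bound for incidence (unknowns counted negative) and an upper bound (unknowns counted positive). A new denominator alone is not enough.
4. Base the transient/persistent rule on the last valid nAb result.
5. Footnote the number of treatment-emergent subjects whose baseline nAb result was NR.

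The cost is a few lines of SAP text and programming, and possibly assaying a few stored Positive-TNR samples. The reported nAb incidence may become a range instead of a single figure.
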